2. INTRODUCTION

2.1 Literature

Surgical operations for the treatment of perianal diseases are a major part of all elective surgical cases. The reduction in the hospitalization time of patients undergoing surgical procedures for benign perianal diseases is to the benefit of both the patient and healthcare provider¹. The importance of 'one day' surgical operations lies in the fact that the patient returns directly to his social and working environment, while the number of occupied hospital beds and the total hospitalization costs are reduced. A typical example is the goal set by NHS, where the 75% of the scheduled operations should consist of 'one day' operations¹. In order to achieve this goal, several obstacles should be dealt with, including the implementation of more efficient and safe surgical techniques. Therefore, this would be associated with a decrease in the operation time, early recovery and faster hospital discharge.

Hemorrhoids is one of the most common benign perianal diseases. According to a recent prospective study² of 976 patients, 38.93% of them suffered from hemorrhoids, with 8.16% and 0.53% being Grade III and IV, according to Goligher classification, respectively. The percentage of the symptomatic patients was, also, significant (44.74%). Symptomatic hemorrhoids, includes bleeding, pruritus, pain, poor hygiene and the presence of palpable hemorrhoid nodules.

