- Complications occurring at 7 days postoperatively:
 - Pain on the basis of the VAS scale. Postoperative pain level at 7 days after surgery, quantified with the use of the VAS scale. Time Frame: 7 days postoperatively
 - Oedema at the operative site. Occurrence of postoperative oedema at the operative site. If such an episode occurs, then it will be defined as=1 'YES' If such an episode does not occur, then it will be defined as=0 'NO'. Time Frame: 7 days postoperatively
 - Hematoma at the operative site. Occurrence of postoperative hematoma at the operative site. If such an episode occurs, then it will be defined as=1 'YES' If such an episode does not occur, then it will be defined as=0 'NO'. Time Frame: 7 days postoperatively
 - Infection at the operative site. Occurrence of postoperative infection at the operative site. If such an episode occurs, then it will be defined as=1 'YES' If such an episode does not occur, then it will be defined as=0 'NO'. Time Frame: 7 days postoperatively
 - Stenosis at the operative site. Occurrence of postoperative stenosis at the operative site. If such an episode occurs, then it will be defined as=1 'YES' If such an episode does not occur, then it will be defined as=0 'NO'. Time Frame: 7 days postoperatively
- Postoperative return to work time. Measurement unit: days. Time Frame: Postoperative period up to 1 month
- Complications occurring at 1 year postoperatively:
 - Pruritus. Occurrence of postoperative pruritus at the operative site. If such an episode occurs, then it will be defined as=1 'YES' If such an episode does not occur, then it will be defined as=0 'NO'. Time Frame: 1 year postoperatively
 - Mucosal proptosis. Occurrence of postoperative mucosal proptosis at the operative site. If such an episode occurs, then it will be defined as=1 'YES' If such an episode does not occur, then it will be defined as=0 'NO'. Time Frame: 1 year postoperatively
 - Perianal nodules. Occurrence of postoperative perianal nodules. If such an episode occurs, then it will be defined as=1 'YES' If such an episode does not occur, then it will be defined as=0 'NO'. Time Frame: 1 year postoperatively
 - Constipation. Occurrence of postoperative constipation. If such an episode occurs, then it will be defined as=1 'YES' If such an episode does not occur, then it will be defined as=0 'NO'. Time Frame: 1 year postoperatively

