 - Constipation. Occurrence of postoperative constipation. If such an episode occurs, then it will be defined as=1 'YES' If such an episode does not occur, then it will be defined as=0 'NO'. Time Frame: 1 year postoperatively
 - Tenesmus. Occurrence of tenesmus. If such an episode occurs, then it will be defined as=1 'YES' If such an episode does not occur, then it will be defined as=0 'NO'. Time Frame: 1 year postoperatively.
 - Reoperation. Occurrence of reoperation. If the patient is reoperated, then it will be defined as=1 'YES' If the patient is not reoperated, then it will be defined as=0 'NO'. Time Frame: 1 year postoperatively
- Disease recurrence rate at 1 year postoperatively. Disease recurrence rate If such an episode occurs, then it will be defined as=1 'YES' If such an episode does not occur, then it will be defined as=0 'NO'. Time Frame: 1 year postoperatively
- Satisfaction level at 1 year postoperatively. Satisfaction level measured at a 0-10 scale. Time Frame: 1 year postoperatively
- Difference in the quality of life of the patient, at 1 month and 1 year postoperatively, compared to the respective preoperative measurements, based on the SF-36 questionnaire, weighted for the Greek. Time Frame: Preoperatively, 1 month postoperatively and 1 year postoperatively.

4. Analysis Set

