4.6 Covariates

The following data will be considered as covariates

- Demographics (Gender, Age, Weight, Height, ASA)
- Symptoms (Proptosis, Bleeding, Pruritus, Pain)
- Hemorrhoid Grade

5. Statistical Methodology

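### Five 1-year complications are scored on any occurrence regardless of preoperative status, and three of them have no planned baseline, so new harm cannot be separated from persisting or recurrent disease

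*Protocol*

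**What the plan says.** Protocol 3.7 and SAP 3.2 carry the same list under "Complications occurring at 1 year postoperatively". Apart from reoperation it holds five items:

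- "Pruritus. Occurrence of postoperative pruritus at the operative site"
- "Mucosal proptosis. Occurrence of postoperative mucosal proptosis at the operative site"
- "Perianal nodules. Occurrence of postoperative perianal nodules"
- "Constipation. Occurrence of postoperative constipation"
- "Tenesmus. Occurrence of tenesmus"

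Each is coded 1 if it occurs and 0 if not. None carries a condition that it be new or worse than before surgery, and the tenesmus item is not even restricted to the postoperative period. Recurrence at 1 year is a separate yes/no endpoint, with no criteria that set it apart from these items.

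Elsewhere the documents treat several of the same items as the disease under treatment. Protocol 2.1 states: "Symptomatic hemorrhoids, includes bleeding, pruritus, pain, poor hygiene and the presence of palpable hemorrhoid nodules". SAP 4.6 lists as covariates "Symptoms (Proptosis, Bleeding, Pruritus, Pain"), beside demographics and hemorrhoid grade.

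The data list in Protocol 3.11 has no preoperative symptoms. Among the endpoints, only SF-36 is explicitly compared with a preoperative measurement.

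**The concern.** A complication rate at 1 year is normally read as harm done by the operation. Under this scoring, three kinds of patient receive the same code: one with a new problem, one whose hemorrhoid symptoms never cleared or came back, and one who was constipated before surgery and still is. The first is harm, the second is treatment failure and the third is background. The same residual disease can also appear under pruritus, proptosis, nodules and recurrence.

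At stake is what the 1-year safety rates mean. An efficacy difference between the techniques could be read as a safety difference, or a true safety difference could be hidden by background cases. Preoperative status cannot be recovered reliably once patients have been operated on, so the gap has to be closed before surgery.

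**Working it through.** **Step 1: which items have a baseline.**

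| 1-year item | Described as a disease feature | Baseline planned |
|---|---|---|
| Pruritus | Protocol 2.1, SAP 4.6 | Implied by SAP 4.6; not in Protocol 3.11 |
| Mucosal proptosis | SAP 4.6 | Implied by SAP 4.6; not in Protocol 3.11 |
| Perianal nodules | Protocol 2.1 (palpable nodules) | None |
| Constipation | No | None |
| Tenesmus | No | None |

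**Step 2: does the analysis plan repair the scoring?** SAP 5.3 compares categorical endpoints with an unadjusted Pearson chi-square test. It also applies logistic regression to all endpoints, but with forward selection, so a baseline symptom may be left out of the model. Where it stays in, it adjusts the odds ratio but does not turn a persisting symptom into a non-event. The N (percentage) that is reported is unchanged.

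**Step 3: unequal background.** No figure in the plan attaches to these items, so only illustrations are possible. Inputs: the remission rates of 72.5% (Doppler arm) and 90% (experimental arm) in Protocol 3.8. Assumptions: non-remission persists to 1 year and shows as the item in question; new onset is 5% in both arms among the remaining patients.

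Rate = b + (1 − b) × new onset, where b is the share with a persisting item.

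- Doppler arm: b = 1 − 0.725 = 0.275; rate = 0.275 + 0.725 × 0.05 = 31.1%
- Experimental arm: b = 1 − 0.90 = 0.10; rate = 0.10 + 0.90 × 0.05 = 14.5%
- Gap: 16.6 points, with no difference in new complications
- Share of counted cases that is persisting disease: 0.275/0.311 = 88% and 0.10/0.145 = 69%

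**Step 4: equal background.** Assumptions: 30 per arm (Protocol 3.8), new onset 5% vs 30%, and the same b in both arms. Power is for the two-sided 5% chi-square test, by exact binomial enumeration. The last column counts new-onset cases only, with patients who had the item at baseline removed and power averaged over the resulting group sizes.

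| b | Rates as scored | Power as scored | Power, new onset only |
|---|---|---|---|
| 0% | 5% vs 30% | 78% | 78% |
| 10% | 14.5% vs 37% | 52% | 73% |
| 20% | 24% vs 44% | 37% | 67% |
| 30% | 33.5% vs 51% | 28% | 61% |

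The fair comparison is within a row. The 78% applies only when nobody has the item before surgery. The 5% vs 30% contrast is also a large one: at 5% vs 20%, power is about 45% even with no background, and 24%, 17% and 13% as scored at b = 10%, 20% and 30%.

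**The case against.** The strongest reply is that the SAP does plan for preoperative symptoms. Pruritus and proptosis are covariates in SAP 4.6, and SAP 5.3 applies regression to every endpoint. This stands. A reader might infer that none of the five items has a preoperative value; the documents do not support that for these two. The provision is incomplete, for the reasons in step 2 of the working, and it does not reach the other three items.

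A second reply is that gastrointestinal disorders are excluded (Protocol 3.3, SAP 4.3), which may remove some patients with earlier bowel complaints. That is fair, but the term is undefined and names neither constipation nor tenesmus. It cannot cover pruritus, proptosis or nodules, which belong to the enrolled disease.

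Third, a reader might infer that background cases necessarily dilute a real difference. That holds only if the background is equal in both arms, and the plan's own remission rates point to unequal background.

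Fourth, randomisation keeps the arm comparison fair as a comparison of symptom prevalence, and neither document defines a composite, so overlap between items inflates no total. Both statements are correct. What remains at issue is how each rate is labelled and interpreted.

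Finally, counting only new cases would have its own faults. Few patients might be at risk for items common before surgery, and an item present at both times may have cleared and returned. Both points stand and shape the fix.

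**Conclusion.** The point holds in this form: the scoring of five 1-year items ignores preoperative status, at least three items describe the treated disease, and three (perianal nodules, constipation, tenesmus) have no baseline in either document. The rates can therefore mix new harm with persisting or recurrent disease and earlier bowel complaints.

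The documents do not state that persisting disease will be counted as harm; it is a consequence that the scoring allows. Its size cannot be derived from them. The 16.6-point gap assumes that 1-month non-remission carries over to 1 year in a single item, with 5% new onset in each arm. The power figures assume a 10% to 30% background, equal between arms. Together they show that the error can run in either direction and need not be small.

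These are secondary endpoints outside the sample size calculation, so the primary endpoint and the 60 patients are unaffected. The change is worth making because it is cheap and cannot be made after surgery.

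**What to change.** 1. Protocol 3.11: add pruritus, mucosal proptosis, perianal nodules, constipation and tenesmus as yes/no items recorded preoperatively.
2. Protocol 3.7 and SAP 3.2: relabel the group *1-year symptoms and complications*.
3. Keep the comparison of each item in all patients by arm. In addition, report each item by arm, split into new-onset (absent preoperatively, present at 1 year) and present at both times. Name the second category *persisting or recurrent*, because a symptom that cleared at 1 month and returned is not persisting.
4. Use the new-onset count when describing surgical complications.

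Cost: five yes/no items at the preoperative assessment, when SF-36 is already collected, plus the case report form and wording changes. The downside is a smaller at-risk group for new onset, possibly very small for items common at baseline such as proptosis and nodules. That is why the all-patient comparison should stay.

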3.8 Sample Size calculation

The calculation of the sample size is based on the primary endpoint. According to the literature, the rate of the remission rate of symptoms, of patients who were submitted to hemorrhoidal artery ligation using ultrasound is 72.5%, while the respective rate of the ligation and hemorrhoidopexy technique is 90%²⁰. Therefore for a non-inferiority trial, with $\alpha= 2,5\%$, $\beta= 80\%$ and a non inferiority limit of 10% , the calculated sample for each group is 30 patients²⁷. Totally, the required number of patients is 60.

3.9 Randomization

The randomization of the patients, between the two groups, will be performed using a software and a 1: 1 allocation ratio will be performed. Furthermore, an opaque envelope, which will contain the allocation group for the specific patient, will be opened preoperatively upon the entry of the patient into the surgical room, thus determining which technique will be applied.

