5.3 Statistical Procedures

The statistical estimations of this study will be based on a per protocol analysis. Prior to any computation, all data will be submitted to a Shapiro-Wilk normality test.

Continuous variables will be compared on the basis of an independent samples t-test, whereas for categorical variables, the Pearson chi-square test will be applied.

The effect of the various patient characteristics on the primary and secondary endpoint will be evaluated by a regression analysis. More specifically, a multiple linear and a logistic regression will be used for continuous and categorical variables, respectively.

Regression analysis will be applied to all distinct endpoints. The validity of the linear regression model will be confirmed by the assessment of the following assumptions:

- Independence of observations, assessed by the Durbin-Watson test
- Linear relationship between the dependent variable and each of the independent variables and between the dependent variable and all the independent variables, collectively.
- Homoscedasticity of the data
- Multicollinearity of the data
- Absence of significant outliers, high leverage points or highly influential points
- Normal distribution of the residuals

A Forward model will be introduced in our multiple linear regression analysis. The proportion of variance explained by our model will be represented by R square. The statistical significance of our model will be evaluated by the F-test. The effect of each independent variable on the dependent outcome will be provided by the respective coefficient and the 95%CI.

Similarly, a Forward model will be applied in our logistic regression analysis. The following assumption will be tested:

- Independence of observations and mutual exclusive and exhaustive categories
- Linear relationship between any continuous independent variable and the logit transformation of the dependent variable

The explained variance will be presented by the Cox & Snell R square and Nagelkerke R square test. The percentage of the correctly classified observations will be also estimated. The statistical significance of each variable will be calculated by the Wald test. The odds ratios of each variable will be also estimated, alongside the respective 95%CI.

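### Hemorrhoid grade is recorded and listed as a covariate, but no planned analysis guarantees a grade-adjusted risk difference to set against the 10-point margin; the loss is modest precision, not bias

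*Protocol*

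**What the plan says.** - **Allocation.** Protocol 3.9 says that randomisation "will be performed using a software and a 1: 1 allocation ratio will be performed". It adds an opaque envelope opened in the operating room. No stratification factor is named, and blocks are neither mentioned nor ruled out.
- **Grade.** Protocol 3.2 admits all Goligher grades up to III. Protocol 3.11 records grade, and SAP 4.6 lists "Hemorrhoid Grade" among the covariates.
- **Arm comparison.** SAP 5.3 compares continuous variables by an independent-samples t-test and categorical ones by Pearson's chi-square. Neither uses grade.
- **Regression.** SAP 5.3 also states: "The effect of the various patient characteristics on the primary and secondary endpoint will be evaluated by a regression analysis". It extends regression to every endpoint, linear or logistic, with forward selection. The logistic output is odds ratios with 95% CIs. Neither allocation nor grade is stated to be forced in. Allocation is named as a model effect only in the repeated-measures ANOVA for SF-36.
- **Size and margin.** In Protocol 3.8, "the calculated sample for each group is 30 patients", with a "non inferiority limit of 10" per cent.

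**The concern.** The non-inferiority question is about an absolute difference in one-month remission, set against 10 points. Grade is a natural candidate for a prognostic factor, and the plan itself lists it as a covariate. With 30 patients per arm, chance can leave one arm with clearly more Grade III disease. If grade affects remission, part of the observed difference in that one trial then reflects grade mix, and readers will ask whether the conclusion survives adjustment.

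The plan cannot be relied on to answer them. The chi-square ignores grade. The logistic model may select grade without arm, arm without grade, or neither, and its odds ratio is not on the scale of the margin. At stake are a little precision and the credibility of the result if the arms turn out unbalanced. The design has no slack: power at 30 per arm is just under 80%.

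**Working it through.** **1. The plan's own figure.** Inputs from Protocol 3.8: "hemorrhoidal artery ligation using ultrasound is 72.5" per cent and "the respective rate of the ligation and hemorrhoidopexy technique is 90" per cent; margin 10 points, taken as absolute; alpha 2.5%, taken as one-sided; the 80% labelled beta, read as power.

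n per arm = (1.960 + 0.842)² × (0.725×0.275 + 0.90×0.10) / (0.175 + 0.10)² = 30.03.

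This agrees with the stated 30 (31 on rounding up). Power at 30 per arm is 79.96%. The SE of the difference is √[(0.1994 + 0.0900)/30] = 9.8 points, so the 95% half-width is 19.2 points. Grade adjustment does not change this calculation.

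**2. How likely is a grade imbalance?** Assume that half the patients are Grade III and that 30 are in each arm. A 20-point difference in Grade III share is 6 patients (6/30).
- Exactly 30 Grade III patients among the 60 (hypergeometric): probability 19.6%.
- Independent binomial counts in each arm: 15.5%.

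Hence about 15-20%, in either direction. The figure depends on the mix: at 80% or 90% Grade III the hypergeometric probability is 10.4% or 2.4%.

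**3. How far does it move the crude difference?** Shift = imbalance × remission gap between grades.
- Gap 10 points: 0.20 × 10 = 2 points.
- Gap 20 points: 0.20 × 20 = 4 points.

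A one-SD imbalance is √(2×0.5×0.5/30) = 12.9 points, so the shift is 1.3 or 2.6 points.

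**4. Which gaps are possible?** With overall remission p and Grade III share w, remission in the lower grades is p + gap × w, which cannot exceed 100%. At p = 90% and w = 50% the largest gap is 10/0.5 = 20 points. A 25-point gap in the experimental arm needs lower overall remission there, for example 85%.

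**5. Does the crude analysis go wrong on average?** Simulation at the margin (72.5% v 62.5%, half Grade III, 200,000 trials per setting) gave bias of about 0. One-sided error was about 2.7% whether the grade gap was 0 or 30 points. The crude interval already carries the variation due to grade.

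**6. What does adjustment gain?** SD of the estimate in points, crude v grade-stratified (Mantel-Haenszel weights), 30 per arm, half Grade III, at least 200,000 trials per setting:

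| Grade gap | True rates | Crude | Stratified | Reduction |
|---|---|---|---|---|
| 10 | 72.5 v 90 | 9.8 | 9.8 | none |
| 15 | 72.5 v 90 | 9.8 | 9.7 | about 1% |
| 20 | 72.5 v 90 | 9.8 | 9.5 | about 3% |
| 25 | 72.5 v 85 | 10.4 | 10.0 | about 4% |

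In patients, 1/0.99² = 1.02 and 1/0.96² = 1.09, so the gain equals about 2% to 9% more patients.

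At the planning effect with a 15-point gap, power rises by about 2 points. Part of that is not real: a Wald-type Mantel-Haenszel interval had one-sided error of 3.0-3.1% at the margin, against 2.7% for the crude interval.

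**The case against.** The strongest reply is that randomisation already deals with chance imbalance: the crude estimate is unbiased and its interval allows for the variation. That stands, and step 5 confirms it. It speaks to patients analysed as randomised; SAP 5.3 analyses per protocol, which is a separate matter.

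A second reply is that the plan does use grade, because SAP 4.6 lists it and SAP 5.3 applies regression to every endpoint, including the primary. A list of baseline covariates also commonly omits the treatment term, so its absence there does not prove that allocation is left out. This stands in part: it would be wrong to say that the plan ignores grade. But a model that may drop either term, and that reports odds ratios, does not guarantee an adjusted difference on the scale of the margin.

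Third, the benefit is small and its inputs are assumed. This also stands. The documents give neither the grade mix nor remission by grade. Protocol 2.1 describes surgery as needed for Grade III-IV, or for Grade II after failed conservative treatment, so the Grade III share may be well above half and imbalance less likely.

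A reader might also infer that allocation is unblocked and that arm sizes could drift apart. Protocol 3.9 is silent on blocks, so this cannot be concluded. Nor do the documents say that grade decides when the Doppler arm adds hemorrhoidopexy; that is plausible but conjecture.

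**Conclusion.** The point holds as a modest gap in the analysis specification. Grade is available and named as a covariate, but no planned analysis is certain to deliver a grade-adjusted risk difference with a CI against the 10-point margin.

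With half the patients Grade III and a remission gap of 10 to 20 points, a 20-point imbalance (probability about 15-20%) moves the crude difference by 2 to 4 points. Adjustment cuts the SD by about 1-4% for gaps of 15 to 25 points, and by nothing measurable at 10. Both the mix and the gap are assumptions.

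Two stronger readings are tempting. One is that the unadjusted primary analysis is biased or has an inflated error rate; the simulation shows that it is not. The other is that imbalance could consume most of the margin. A 6-point shift from a 20-point imbalance needs a 30-point grade gap in both arms. With half the patients Grade III and 90% remission in the experimental arm, that would require 105% remission in the lower grades. The primary analysis is not invalidated.

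**What to change.** **SAP 5.3, primary endpoint.** Prespecify the primary analysis as the remission risk difference stratified by grade (I-II v III), with a two-sided 95% CI whose lower limit is compared with minus 10 points. Choose an interval with adequate small-sample coverage, such as a stratified score-type interval, and check it by simulation near 72.5% v 62.5% before fixing it. The simple Mantel-Haenszel Wald interval runs at about 3% one-sided error. State what is done if a grade stratum is nearly empty in one arm.

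**SAP 5.3, other endpoints.** Force allocation and grade into the models instead of leaving them to forward selection. Where events are too few for a logistic model with two terms, name the fallback. Forward selection can remain as exploratory work on patient characteristics.

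**Protocol 3.9, optional.** If enrolment has not begun, the allocation list can be stratified by grade. This adds almost nothing beyond adjustment: with a 15-point gap the SD goes from about 9.7 to 9.6. It needs two envelope sets and grade written down before the envelope is opened.

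**Cost.** A few lines in the SAP, slightly more analysis work and the choice of an interval. No extra patients or data are needed.
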